### 4.2.2 Clinical Data

A systematic review investigating long-term hearing outcomes in COM patients treated under the current standard of care has been undertaken (28). The systematic review assessed literature published between 2008-2018 in order to assess the clinical success rate of COM treatments in restoring hearing loss (based on an air-bone gap (ABG) closure within 20 dB) at a minimum follow up time of 12-months in both adult and paediatric patients. Key outcomes from the systematic literature review indicated that 30.0% of patients have a post-operative air bone gap of  $\geq 20$  dB. Data also show that 14.7% of patients have post-operative complications, including 7.0% of patients in which a perforation of the tympanic membrane persisted at long-term follow up.

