### 7.2.1 Inclusion Criteria

Subjects must meet all of the inclusion criteria described below to be eligible for this clinical investigation.

1. Adult subjects, 18 years or older.
2. Subjects with conductive or mixed hearing loss.
3. Subjects with historically documented diagnosis of Chronic Otitis Media (COM) with or without cholesteatoma in the operated ear.
4. Subjects who have undergone primary tympanoplasty type I-V to improve hearing between 2010-2016.
5. Subjects with a PTA4 air-bone gap  $\geq 30$  dB OR PTA4 air-bone gap between 25-30 dB with an air conduction threshold PTA4  $\geq 40$  dB HL within 12 months after primary tympanoplasty in the operated ear.
6. Subjects who have been recommended by their health care professional to try a hearing aid to improve hearing in the operated ear.
7. Pre-op audiogram, maximum 1 year prior to the primary tympanoplasty, and post-op audiogram for the primary tympanoplasty are available.
8. Aided audiogram, unaided if no hearing device is used, available between 2018 and the point of enrolment.
9. Subjects are fluent in the language used for study questionnaires: German, French, Spanish.
10. Subjects are willing and able to provide written informed consent.
11. Medical Record data is available throughout the defined data search period, from primary tympanoplasty to point of enrolment.

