### 7.3.2.2 Study data from medical records

The medical record search for data extraction can start in parallel to the questionnaires/survey being answered.

Data to be collected from the medical records include:

- Demographics and hearing/device history information
- Pre- and post-primary tympanoplasty air and bone conduction audiograms (unaided and when applicable aided and PTA4 at minimum)
- Latest available (as per inclusion criteria) air and bone conduction audiograms (unaided and when applicable aided and PTA4 at minimum)
- COM-related contacts with health care providers for the operated ear (including name and number of interventions and/or procedures, medications and therapies, examinations and Middle Ear Risk Index factors and surgical outcomes where applicable)

More details on the information to be collected can be found in **Appendix 1**.

It might be the case in a few sites, that the required audiograms for some subjects were collected in a hearing aid partner centre/shop and not in the clinic itself. For these situations, clinics will reach out to the responsible audiologist and request a copy of the test.

For analysis, health care contacts, interventions and/or procedures will be coded using the ICD-10 coding system. Medication will be coded according to WHO CC ATC.

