## 9.8 Exploratory Endpoint Analyses

### Middle Ear Risk Index factors

The Middle Ear Risk Index (MERI) will be used to guide the extraction of middle ear status variables from the medical records (40). If available, pre-operative factors collected from the medical records will be used to populate the MERI, generating a risk score for individual subjects by summing the corresponding risk factor scores defined within each section of the index. Subjects will be stratified into a low-medium-risk group (MERI: 0–7) and a high-risk group (MERI: 8–15). The relationship between pre-operative factors corresponding to those contained in the MERI on the success rate of tympanoplasty, based on post-operative ABG, will be investigated using a binary logistic regression model. The Spearman correlation coefficient will be used to determine relationships between pre-operative factors and their influence on post-operative outcomes.

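### The MERI analysis in section 9.8 omits the pre-operative air-bone gap, so its estimates are total associations that cannot show a factor's influence beyond starting severity; a baseline-adjusted model beside it would be a cheap improvement.

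*Combined protocol and SAP*

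**What the plan says.** Section 9.8 (Middle Ear Risk Index factors) names its explanatory variables as follows: "The relationship between pre-operative factors corresponding to those contained in the MERI". Their relationship "on the success rate of tympanoplasty, based on post-operative ABG, will be investigated using a binary logistic regression model". A second analysis follows: "The Spearman correlation coefficient will be used to determine relationships between pre-operative factors and their influence on post-operative outcomes". Neither sentence names the pre-operative ABG or any other adjustment variable, and section 9.8 gives no cut-off for success.

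The baseline value is nevertheless at hand. Inclusion criterion 7 (section 7.2.1) requires: "Pre-op audiogram, maximum 1 year prior to the primary tympanoplasty, and post-op audiogram for the primary tympanoplasty are available". Section 7.3.2.2 extracts "Pre- and post-primary tympanoplasty air and bone conduction audiograms", with PTA4 as the minimum, so a pre-operative PTA4 ABG can be derived for each operated ear. The MERI factors themselves are collected only where available.

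Two other places bear on the size of the problem. Criterion 5 admits a post-operative ABG of 30 dB or more, or a "PTA4 air-bone gap between 25-30 dB with an air conduction threshold PTA4" of at least 40 dB HL. The only ABG definition of success in the document is in section 4.2.2 (background review): "based on an air-bone gap (ABG) closure within 20 dB".

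**The concern.** The pre-operative gap is the baseline value of the outcome. An ear that starts with a larger gap can end with a larger one even if surgery closed it equally well. If a middle-ear factor goes with a larger starting gap, an unadjusted model credits the factor with the effect of the starting gap. The documents do not list the MERI items, so which factors behave this way is an assumption. Section 4.1 does name ossicular discontinuity as a major cause of hearing loss in this disease, so the link is plausible for ossicular factors.

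Section 9.8 speaks of the influence of factors on outcome and of the success of the operation, and section 4.3 wants the study to inform treatment decisions. A reader of the results would want to know whether a factor marks a worse start or a worse surgical result. The plan as written cannot separate the two.

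**Working it through.** **Plan's own figure.** There is none for this regression: no alpha, power or effect size is stated, and hypotheses are marked as not applicable (section 9.3). The only design calculation, in section 9.4, concerns something else. It does reproduce: 1 − (1 − 0.02)^200 = 0.982, against 98% stated.

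**Algebra.** Let F be the factor (0/1), pre = m + s·F + u, and post = a + b·pre + d·F + e. Here s is the shift in starting gap, b the slope of post on pre, and d the direct effect. Substituting, the coefficient of F without pre is d + b·s; with pre in the model it is d. For a pure marker d = 0, so the unadjusted coefficient before any selection is b·s. Examples are 0.4 × 5 = 2.0 dB and 0.5 × 10 = 5.0 dB. If b = 0 it is zero.

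**Simulation 1: how often a pure marker reaches two-sided p < 0.05.** All inputs are assumed: 200 ears with post-operative ABG ≥ 25 dB, factor prevalence 40%, pre-operative SD 10 dB, residual SD 9 dB, d = 0, 600 runs per setting. The Monte Carlo SE at 5% is √(0.05 × 0.95/600) = 0.9 points. The cut-offs of 30 and 35 dB are hypothetical, since section 9.8 gives none.

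| Shift s (dB) | Slope b | b·s (dB) | Unadjusted, success < 30 dB | Unadjusted, success < 35 dB |
|---|---|---|---|---|
| 5 | 0.4 | 2.0 | 6.8% | 8.3% |
| 8 | 0.4 | 3.2 | 17.3% | 18.3% |
| 8 | 0.6 | 4.8 | 30.0% | 37.3% |
| 10 | 0.5 | 5.0 | 33.2% | 40.5% |

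With the pre-operative ABG as covariate the logistic rate was 4.8-6.2% throughout. With post-operative ABG analysed in dB, it was 10.7-54.5% unadjusted and 3.8-6.3% adjusted. A repeat gave 9-29% (30 dB) and 9-37% (35 dB) unadjusted, against 3-6% adjusted. It also gave 8-10% at s = 8, b = 0.2, and no inflation at b = 0.

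**Simulation 2: odds ratio for success of a pure marker (true conditional value 1.0).** Assumed: pre-operative ABG mean 32, SD 10 dB; post-operative mean 22 dB, residual SD 10 dB; latent correlation of factor with starting gap 0.3 or 0.6.

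| Slope | No selection, success ≤ 20 dB | Criterion 5 applied, success ≤ 30 dB |
|---|---|---|
| 0 | 1.01 / 1.00 | 1.00 / 1.00 |
| 0.2 | 0.86 / 0.73 | 0.93 / 0.86 |
| 0.5 | 0.71 / 0.50 | 0.86 / 0.69 |

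Adding the pre-operative ABG brought every entry back to about 1.0. In the right-hand column, the chance of reaching p < 0.05 at 200 subjects was 5-22% unadjusted.

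**Limits set by criterion 5.** Every qualifying post-operative gap is at least 25 dB, so with success at 20 dB there are 0 successes in 200 and neither model can be fitted. On the dB scale, truncated at 25 dB, a true direct effect of 5 dB came out at 2.0-2.3 dB in the adjusted model.

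**Precision.** For a true direct effect unrelated to baseline, adjustment raised power from 27% to 38% at the 30 dB cut-off (assumed inputs).

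**The case against.** The strongest reply is that the objective is prognostic. Section 6.3 asks for a scoring system that classifies severity and relates it to surgical outcome. Such a score may use the total association, and a factor that predicts a poor result through a larger starting gap is a valid predictor. On an absolute scale of success the association is real. Before selection, under assumed inputs, success at 20 dB was 45-47% without the factor and 28-37% with it. The unadjusted rejection rates are then power against a true total association, and count as errors only if the claim is an effect beyond the starting gap. This stands.

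It is also fair that the gap may lie on the causal path. If ossicular damage causes the gap, adjusting for it removes part of the damage's real effect. So the tempting remedy of resting every statement about success on the adjusted figures goes too far: it could suppress real severity markers.

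Three smaller points stand too. The plan does not forbid adjustment. The Spearman sentence is not confined to ABG, and partialling out the starting gap has no obvious motive for outcomes such as otorrhoea or perforation (Appendix 1). Finally, the selection on outcome and the undefined success criterion are more basic defects, which adjustment leaves untouched.

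What the reply does not remove is the wording of section 9.8 about influence on outcomes. The unadjusted analysis cannot support that wording, and the variable that would help is already collected.

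**Conclusion.** The point holds in a limited form. The planned analyses estimate total associations. They suit a severity score but do not show that a factor influences the surgical result beyond starting severity.

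Under assumed inputs with slopes of 0.2-0.6, a pure marker is significant in about 7-41% of studies unadjusted and about 4-6% adjusted. The documents give neither the slope nor the link between factor and starting gap, and with a slope of zero nothing is inflated.

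A reader might infer that the study will report such markers as lowering tympanoplasty success. The documents do not support that: the size is unknown, and in most simulated logistic analyses the marker did not reach significance. Nor do they support treating the unadjusted analysis as wrong in itself. For an exploratory endpoint with data collected only if available, this is a cheap improvement.

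**What to change.** In section 9.8, keep the planned unadjusted analysis and add:

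- the same regression with the pre-operative PTA4 ABG of the operated ear (dB, continuous) as a covariate;
- partial rank correlations controlling for pre-operative ABG, where the outcome is post-operative ABG;
- a sentence assigning the results: unadjusted for the severity score, adjusted for any statement that a factor influences the surgical result beyond the starting gap;
- a sentence stating that, because criterion 5 admits only post-operative gaps of at least 25 dB, effect sizes from both models are attenuated. It should add that adjustment repairs neither this nor the impossibility of meeting the 20 dB definition in section 4.2.2.

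The cost is a few sentences and one more model to report, with no new data. For factors that act through the gap, the adjusted coefficient is only the part beyond it, which is why both results should be shown. The change is best made when success and the audiogram that determines it are defined.

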Exclusion criteria	
 
1. Subjects are unable or unwilling to comply with the requirements of the study as determined by the investigator.
 
2. Investigator site personnel directly affiliated with this study and/or their immediate families; immediate family is defined as a spouse, parent, child, or sibling.
 
3. Cochlear employees or employees of Contract Research Organizations or contractors engaged by Cochlear for the purposes of this study.
 

Objectives and Endpoints	
Primary Objective	Primary Endpoint
Map health care utilisation.	
Categorical data collected from primary tympanoplasty to time of enrolment:
 
 
- Number and type of contacts with health care providers
 
- Number and type of interventions and/or procedures (medical examinations, surgical procedures, hearing rehabilitation)
 
- Number and type of medications and therapies
 

Secondary Objectives	Secondary Endpoints
Characterise long-term hearing performance.	
Pre- and post-primary tympanoplasty and a third assessment between 2018 and time of enrolment:
 
 
- PTA4 (0.5, 1, 2 and 4 kHz) for both air and bone conduction, under unaided and when applicable aided conditions.
 

Estimation of health care costs.	
From primary tympanoplasty to time of enrolment:
 
 
- Unit cost
 

Collect socio-economic data, demographics and information on service utilisation.	
At time of enrolment:
 
 
- Client Service Receipt Inventory (CSRI).
 

Assess patient reported outcomes.	
At time of enrolment:
 
 
- Health Utilities Index Mark III (HUI3)
 
- Chronic Otitis Media Outcome Test-15 (COMOT-15)
 
- Speech, Spatial and Qualities of Hearing Scale (SSQ-12)
 

Validate the COMOT-15 in French and Spanish.	Responses from a minimum of 30 subjects per language and audiograms collected within one year of questionnaire completeness.

Exploratory Objectives	Exploratory Endpoints
Develop scoring system to classify severity of middle ear status and relate to surgical outcome.	Middle Ear Risk Index factors (preoperative status, intraoperative findings) and surgical outcomes, if available.

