### 7.2.3 Number of Subjects Required

200 subjects will be enrolled in the clinical investigation, with a maximum estimated overhead of 10% taking into consideration the simultaneous recruitment at all sites. It is estimated that approximately double the size will need to be screened (30) to meet this sample size. Additionally, to meet the

validation requirements on the COMOT-15, a minimum of 30 subjects (29) with complete data are required at both the Spanish and French clinics (see section 7.3.2.1 for detailed justification).

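### Section 9.8 reduces post-operative air-bone gap to success or failure in its only regression, although the dB value can be derived for eligible subjects; an adjusted dB model would use more of the data, within the limits set by criterion 5

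*Combined protocol and SAP*

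**What the plan says.** The exploratory objective in the synopsis and section 6.3 is: "Develop scoring system to classify severity of middle ear status and relate to surgical outcome". Section 9.8 describes the analysis in four steps.

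- Scoring, subject to data: "If available, pre-operative factors collected from the medical records will be used to populate the MERI".
- Grouping: "Subjects will be stratified into a low-medium-risk group (MERI: 0–7) and a high-risk group (MERI: 8–15". No test or model is attached to this sentence.
- Regression: "The relationship between pre-operative factors corresponding to those contained in the MERI" is studied "on the success rate of tympanoplasty, based on post-operative ABG, will be investigated using a binary logistic regression model". No dB cut-off for success is given, the audiogram to be used is not named, and pre-operative ABG is not listed as a covariate.
- Correlation: "The Spearman correlation coefficient will be used to determine relationships between pre-operative factors and their influence on post-operative outcomes". The variables on either side are not named further.

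The audiometric data are secured by eligibility: "Pre-op audiogram, maximum 1 year prior to the primary tympanoplasty, and post-op audiogram for the primary tympanoplasty are available" (criterion 7). Section 7.3.2.2 collects air- and bone-conduction thresholds, with PTA4 as the minimum, before and after surgery, so ABG in dB follows by subtraction. Criterion 5 requires a PTA4 ABG of 30 dB or more within 12 months after surgery, or 25 to 30 dB with an air-conduction PTA4 of at least 40 dB HL. Every eligible subject therefore had an ABG of at least 25 dB on the qualifying audiogram.

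**The concern.** A binary outcome treats all ABG values on one side of the cut as equal. Where an association is modest, factor effects are then estimated less precisely, and real prognostic factors are easier to miss. This matters for the stated objective because a scoring system needs factor weights that are adjusted for one another, and the logistic model on the cut outcome is the only planned analysis that could supply them. The plan gives no reason for leaving the dB scale. It also leaves out pre-operative ABG, a natural adjustment variable that criterion 7 makes available.

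**Working it through.** **The plan's own figure.** Section 9.8 states no power or sample size. The only sizing figure is in section 9.4: a 98% chance that 200 subjects show the least likely intervention at least once. It reproduces: 1 − (1 − 0.02)^200 = 98.2%, and 99.5% at the quoted rate of 2.63%. It says nothing about the MERI analysis.

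**Inputs.** N = 200 is from section 7.2.3 and is a best case, because MERI factors are collected only if available. All other inputs are assumptions: two-sided alpha 0.05, correlation r between MERI and ABG, and success share s.

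**Step 1: cutting the outcome only, no enrolment selection.**

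Full scale: power = Φ(atanh(r)·√(N − 3) − 1.96).

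Outcome cut: replace r by r·k, where k = φ(z_s)/√(s(1 − s)) and z_s is the normal quantile at s. This gives k = 0.798, 0.759 and 0.653 for s = 50%, 30% and 15%.

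Example with r = 0.20:
- Full scale: 0.2027 × 14.04 − 1.96 = 0.885, power 81%.
- Cut at s = 50%: r·k = 0.160, and 0.161 × 14.04 − 1.96 = 0.30, power 62%.

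| r | Full scale | Cut, s = 50 / 30 / 15% | Loss (points) |
|---|---|---|---|
| 0.15 | 56% | 39 / 36 / 28% | 17 / 20 / 28 |
| 0.20 | 81% | 62 / 57 / 45% | 19 / 24 / 36 |
| 0.25 | 95% | 81 / 77 / 64% | 14 / 18 / 31 |

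The range is 14 to 36 points. At r = 0.50 the loss is 0 to 1 point. With MERI data on only 100 subjects and r = 0.20, the loss is 16 to 26 points.

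**Step 2: what Spearman recovers.** Simulation without selection used N = 200, an integer MERI score with mean 6 and SD 3, and ABG with mean 16 and SD 8 dB, so that about 69% fall within 20 dB.

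| r | Linear | Spearman | Logistic, full score |
|---|---|---|---|
| 0.15 | 58% | 53% | 38% |
| 0.20 | 80% | 76% | 57% |
| 0.25 | 96% | 93% | 77% |
| 0.30 | 99% | 99% | 92% |

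If Spearman is applied to uncut ABG and score, it loses at most 5 points for a single pairwise test.

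**Step 3: with criterion 5.** ABG is restricted to at least 25 dB, and success is assumed to mean below 30 dB. Over r = 0.15 to 0.30, linear power is about 16% to 64% and the gain over logistic regression about 4 to 26 points, depending on the assumed ABG distribution. Fitted slopes shrink to about 20% to 30% of their unselected size. A separate run that kept higher power gave linear 29 / 45 / 63 / 83% against logistic 17 / 25 / 37 / 54% at r = 0.15 / 0.20 / 0.25 / 0.30, a gain of 12 / 20 / 26 / 29 points. The direction is stable; the size is not.

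**Step 4: the only success definition in the documents.** Section 4.2.2 reports a systematic review that used ABG closure within 20 dB. Criterion 5 puts every qualifying value at 25 dB or more. With that definition on that audiogram there are no successes, and the logistic model could not be fitted.

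**The case against.** The strongest reply is that power is not a design target here. Section 9.1 calls the statistics descriptive, section 9.3 sets no hypotheses, and section 9.4 says the study does not test strengths of association. That stands: this is a matter of efficiency in an exploratory analysis, and the plan fails no target of its own.

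A second reply is that Spearman already keeps the scale. For a single pairwise test this is largely right, if it is applied to ABG in dB, which section 9.8 does not say. It does not serve the objective fully, because simple rank correlations give no mutually adjusted weights, no adjustment for pre-operative ABG and no effect in dB.

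A third reply is that a dB model inherits the selection made by criterion 5. That also stands. The model avoids an empty outcome class, but its slopes are attenuated and describe only patients with a residual gap.

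Two stronger readings are tempting. A reader might infer that the 0–7 / 8–15 grouping adds a second loss of power. The text does not put the grouped score into any model; the regression predictors are the MERI factors. A reader might also infer that the logistic model is bound to fail for lack of successes. Section 9.8 neither adopts the 20 dB definition nor names the audiogram, so that result holds only for that combination.

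**Conclusion.** The point holds as a low-severity, inexpensive improvement. The only planned regression discards the dB scale of an outcome that the study can derive, and the planned correlations do not replace an adjusted model for building a score. Without enrolment selection, and under the assumptions in step 1, cutting the outcome costs about 14 to 36 points of power for correlations of 0.15 to 0.25, and almost nothing for strong ones. In the population actually enrolled, both models have lower power and the gain is roughly 4 to 26 points, with 29 the largest single value seen. None of these figures is fixed by the documents, since effect size, alpha, success share, ABG distribution and the number with MERI data are all unstated. A reader might take the step 1 range as the loss in this trial, independent of criterion 5. The documents do not support that, because criterion 5 truncates the same outcome.

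**What to change.** In section 9.8, for subjects with MERI data available:

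- Make linear regression of post-operative PTA4 ABG in dB on the MERI factors the main MERI analysis. Fit a separate model on the numeric 0–15 score. Include pre-operative ABG as a covariate in both.
- Use robust standard errors, or a proportional-odds model if ABG is skewed.
- Report dB per MERI point with a 95% confidence interval.
- Keep success proportions and the 0–7 / 8–15 groups as descriptive tables.
- State that criterion 5 truncates the outcome, so that slopes are attenuated and apply only to patients with a residual ABG of at least 25 dB.

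The cost is a wording change and one extra model form, with no new data or subjects. The downside is that the main result is in dB and not an odds ratio for success; the success proportion can still be tabulated.
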